6.8.3 Laboratory data

Clinical laboratory values will be expressed in standard international (SI) units. Laboratory data collected and recorded as below the limit of detection will be set equal to the lower limit of detection for the calculation of summary statistics.

For each continuous clinical laboratory parameter (including hematology, serum chemistry, coagulation studies and thyroid and liver function tests) from the central laboratory descriptive statistics will be presented for the actual values, change from baseline, and percent change from baseline by visit. The descriptive statistics under the original dose and regimen will be provided from the LTE14762 study baseline up to the last assessment before the 2017 clinical hold. The baseline used for this analysis is LTE14762 study baseline. Similar by-visit summary will be provided under the revised dose and regimen from the dose resumption after 2020 voluntary dose pause up to the end of study. There are 2 baselines considered for this analysis, which are LTE14762 study baseline and dose resumption baseline on or before the dose resumption after the 2020 voluntary dose pause.

In order to address impact of 2017 and 2020 dose interruption, additional spaghetti plots using actual values will be provided for below laboratory parameters:

4. Alanine Aminotransferase (ALT),
5. Aspartate Aminotransferase (AST),
6. Total Bilirubin,
7. Alkaline Phosphatase,
8. D-Dimer,
9. Prothrombin Fragments 1 + 2 and
10. Fibrinogen.

All the assessments from central laboratory, including assessments performed during the 2017 and 2020 dose interruption periods, will be used for the plot. For those assessments collected during the 2017 and 2020 dose interruption periods, a different color will be used to distinguish these periods.

For each continuous laboratory parameter, results will be categorized as low, normal, or high based on the laboratory normal ranges (when available).

Listings will be produced for all participants with abnormal liver function tests defined as an ALT $>3 \times$ ULN or $3 \times$ Baseline (for those participants with abnormal values at baseline), or AST $>3 \times$ ULN or $3 \times$ Baseline (for those participants with abnormal values at baseline, at any time point. ("Baseline" here means LTE14762 baseline.) These listings will include each of the assessments specified in Tables 8 and 9 of the Protocol (Amendment 9).

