10.2.6 Safety Analyses

Adverse events will be summarized by the MedDRA System Organ Class and Preferred Term. Incidence of treatment-emergent adverse events (TEAEs; those events that started after exposure to study drug or worsened in severity after dosing) will be presented by dose level and overall. Incidence of TEAEs will also be presented by maximum severity and relationship to study medication or underlying hemophilia. The incidence of SAEs and AEs leading to discontinuation of treatment will also be tabulated. By-patient listings will be provided for deaths, SAEs, and events leading to discontinuation of treatment.

Descriptive statistics will be provided for clinical laboratory data (including biochemistry, hematology, urinalysis, and coagulation) and vital signs data, presented as both actual values and changes from baseline relative to each on-study evaluation. Laboratory shift tables from baseline to worst values will be presented. Baseline will be defined as the last observation on or before Day 1. Abnormal physical examination findings, 12-lead ECG data, and antidrug antibody results will be presented in a by-patient data listing. Antidrug antibody results will also be tabulated.

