2 STUDY OVERVIEW

2.1 SYNOPSIS OF STUDY DESIGN

LTE14762 is an open-label extension (OLE) study to evaluate long-term safety, tolerability, and efficacy of subcutaneously administered fitusiran in patients with moderate or severe hemophilia A or B, with or without inhibitory antibodies to factor VIII or factor IX, who previously tolerated dosing in the parent study, TDR14767(formerly ALN-AT3SC-001). The primary objective of this study is to evaluate the long-term safety and tolerability of fitusiran, assessed by incidence, severity, relatedness, and seriousness of adverse events, and laboratory assessments.

TDR14767(ALN-AT3SC-001) was a Phase 1 study that evaluated the safety, tolerability, and PK of fitusiran in healthy male volunteers and male patients with hemophilia A or B.

TDR14767(ALN-AT3SC-001) was conducted in 4 parts:

Part A: a randomized, placebo-controlled, single-blind single-ascending dose (SAD) phase in healthy subjects

Part B: an open-label, multiple-ascending dose (MAD) phase in patients with moderate to severe hemophilia A or B without inhibitors

Part C: an open-label, exploratory multiple dose (MD) phase in patients with moderate to severe hemophilia A or B without inhibitors

Part D, an open-label MD phase in patients with moderate to severe hemophilia A or B with inhibitors.

Study TDR14767(ALN-AT3SC-001) was completed on 20 July 2017 (last patient last visit).

Patients who received all 3 doses of study drug in TDR14767(ALN-AT3SC-001) and completed required study visits in the parent study were eligible for participation in LTE14762. All enrolled participants will initially receive a 50 mg or 80 mg dose of fitusiran once monthly.

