5.2 GENERAL METHODS

Both efficacy and safety analysis under the original and revised dose regimens will be analyzed separately, unless otherwise specified. The data collected during the 2020 voluntary dose pause will be analyzed along with the pre-pause data.

A significant dose is defined as any single dose of fitusiran that is greater than or equal to 20 mg. Before the voluntary dose pause, the analysis period for efficacy endpoints starts from the date of first significant dose up to the earlier of 2020 voluntary dose pause date or the last day of study follow-up. For safety endpoints, the analysis will be performed based on LTE14762 study period data only up until the dose restart date. Date of first significant dose in the TDR14767(ALN-AT3SC-001) and LTE14762 study/studies will be designated as Treatment Day 1; there will be no Treatment Day 0. Participants who receive doses (either weight-dependent or weight-independent) of at least 20 mg but less than 75 mg will be “classified” as “50 mg” participants, while participants receiving doses of greater than or equal to 75 mg will be “classified” as “80 mg” participants (except PK analysis in which actual dose on Day of PK sample collection will be used). However, for purposes of efficacy and safety analyses and summaries in the final CSR report for the LTE14762 study, the classification of each participant under the original dose and regimen will be according to the fixed dose to which they are eventually taken by the end of the LTE14762 study original dose period. For example, participants who received a 50 mg dose in TDR14767(ALN-AT3SC-001) or LTE14762 and then were switched to 80 mg dose at some point in time during the LTE14762 study, are classified in the LTE14762 study as “80 mg” participants (except for PK analyses). Treatment after the volunteer dose pause will be treated as each participant’s treatment sequence.

[figure not shown]
Treatment Days under the original dose and regimen will be calculated as evaluation date – first significant dose date +1 and pre-treatment days will be calculated as evaluation date – first significant dose date. (The pre-treatment day formula applies when evaluation date < first significant dose date; ie, for example, there will be pre-treatment Days ... -3, -2, -1, then treatment Day 1, 2, 3, 4, ...; there is no “pre-Treatment Day 0” nor is there any “Treatment Day 0”).

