We also define Study Days in the LTE14762 study as the number of days from first significant dose in LTE14762 and calculate similarly as the Treatment Days. For participants who received first significant dose in LTE14762, the Study Days is the same as the Treatment Days.

For participants under the revised dose and regimen, both efficacy and safety data will be analyzed from the dose re-start Day 1 up until the last day of study follow-up.

Treatment day after the dose re-start will be calculated as evaluation date – first dose date after dose re-start + 1 (days). It should be not applicable for assessments before the dose re-start. A summary of study periods and start day in analysis is outlined in [Figure 1](#)

Figure 1 Study periods and analysis start day summary

	Original dose and regimen	2017 clinical hold/2020 voluntary dose pause	Revised dose and regimen
Efficacy analysis	Starts from first significant dose of fitusiran in TDR14767(ALN-AT3SC-001) or LTE14762 and in terms of treatment days.	Starts from the 29th days after last dose date before the hold/pause	Starts from first dose date of revised dose and regimen and in terms of treatment days
Safety analysis	Starts from first significant dose of fitusiran in LTE14762 and in terms of study days	Starts from the day after last dose date before the hold/pause and in terms of study days	Starts from first dose date of revised dose and regimen and in terms of study days

Summary statistics will be reported by analysis visits defined in [Section 5.10](#) below. Unless otherwise noted, tables under both the original and revised dose regimens will be presented by hemophilia type, inhibitor type and overall. Participants who received a significant dose in TDR14767(ALN-AT3SC-001) will be considered as a subgroup in the analysis under the original dose and regimen. Details will be specified in the [Section 6.11](#).

Categorical data summary will include the number and percentage of participants within each category, with a category for missing data. Continuous data summary will include descriptive statistics - the number of participants, mean, median, standard deviation (SD), first quartile (Q1), third quartile (Q3), minimum, and maximum. The precision of the measurement for each continuous variable will be used to determine the number of decimal places to present in tables, figures and derived listings. Minimum and maximum values will be reported with the same

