6.8 SAFETY ANALYSES

Safety analyses will be conducted using the safety analysis set 1 and safety analysis set 2. Only the safety data occurred in LTE14762 will be summarized unless specified otherwise.

Safety analysis under the original dose and regimen (i.e. before the 2020 voluntary dose pause) and the revised dose and regimen (i.e. after the 2020 voluntary dose pause) will be analyzed separately. The additional baseline prior to the revised dose regimen administration will be implemented for data collected under the revised dose and regimen. Similar descriptive summaries in reference to the additional baseline will be provided for laboratory, vital sign and ECG endpoints.

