6.8.4 Vital signs and physical examination

Descriptive statistics will be provided for vital signs, including blood pressure, pulse rate, oral body temperature and respiration rate. For data under the original dose and regimen, the descriptive summary will be provided from the LTE14762 study baseline up to the 2017 clinical dose pause. For data under the revised dose, the summary will be provided from the dose resumption up to the end of study. A summary table of PCSA will be provided. Abnormal PE results will be listed. All the vital sign and physical examination summary tables will not include assessment taken during the major surgery period. These results will be presented in listings with identifier of major surgery.

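### Original-regimen laboratory, vital-sign and ECG summaries stop at the 2017 hold and resume only after the 2020 pause, leaving more than three years in neither block

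*SAP*

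**What the plan says.** **Where the summaries stop and restart.** For laboratory data, SAP 6.8.3 states that the original-regimen descriptive statistics (actual value, change and percent change from baseline, by visit) "will be provided from the LTE14762 study baseline up to the last assessment before the 2017 clinical hold". For vital signs, SAP 6.8.4 states that "the descriptive summary will be provided from the LTE14762 study baseline up to the 2017 clinical dose pause", and SAP 6.8.5 uses the same sentence for ECG. In all three sections the revised-regimen block begins at dose resumption after the 2020 pause. No section defines a block for dosing between the 2017 hold and the 2020 pause.

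**What the rest of the SAP says.** SAP 6.8 places the dividing line elsewhere: "Safety analysis under the original dose and regimen (i.e. before the 2020 voluntary dose pause") is one block and everything after that pause is the other. SAP 5.2 agrees: "For safety endpoints, the analysis will be performed based on LTE14762 study period data only up until the dose restart date", and "The data collected during the 2020 voluntary dose pause will be analyzed along with the pre-pause data".

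**What the protocol says.** Protocol 10.2.6 commits to descriptive statistics for laboratory and vital-sign data "presented as both actual values and changes from baseline relative to each on-study evaluation", and to laboratory shift tables from baseline to worst value. For ECG it commits only to a listing.

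**The concern.** The primary objective is long-term safety and tolerability, which SAP 2.1 says is "assessed by incidence, severity, relatedness, and seriousness of adverse events, and laboratory assessments". The omitted years are the later part of exposure to the monthly regimen that was replaced because of thrombotic risk. A gradual shift in haematology, renal function, coagulation or blood pressure that crossed no alert threshold would appear in no by-visit summary for 2017 to 2020.

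The tables that might have offset this are also reduced: SAP 2.6 removes the laboratory shift tables in favour of potentially clinically significant abnormality (PCSA) tables. The revised-regimen tables do use the LTE14762 baseline. With the middle years blank, however, they cannot show whether a change seen after restart arose before or after the regimen changed. Participants who never restarted are outside Safety analysis set 2, so their post-hold values enter no by-visit table.

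**Working it through.** The documents give no figure for the length of the gap, so there is none to reproduce. The inputs are calendar dates and scheduled visit days.

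**Inputs**
- First enrolment: 08-Oct-2015 (SAP 2.5)
- 2017 hold reference date: 01-Sep-2017 (SAP 6.8.1, Table 4)
- 2020 pause reference date: 31-Oct-2020 (Table 4)
- Restart reference date: 26-Jan-2021 (Table 4)
- Scheduled day of Month m = 30m + 1, window ±7 (Protocol Tables 1 and 2)

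**Length of the gap** (days ÷ 365.25)

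| Span | Days | Years |
|---|---|---|
| First enrolment to hold | 694 | 1.90 |
| Hold to start of 2020 pause | 1,156 | 3.16 |
| 2020 pause to earliest restart | 87 | 0.24 |
| Hold to earliest restart | 1,156 + 87 = 1,243 | 3.40 |
| First enrolment to start of 2020 pause | 694 + 1,156 = 1,850 | 5.07 |
| First enrolment to earliest restart | 1,850 + 87 = 1,937 | 5.30 |

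The hold-to-pause span is 1,156 / 1,850 = 62% of calendar time from first enrolment to the 2020 pause. SAP 5.2 assigns the 87 pause days to the pre-pause data, yet they too are in neither block.

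**Time on drug within the gap.** The hold dates in SAP 6.3 are redacted. Assuming a hold of 84 to 180 days:
- 1,156 − 84 = 1,072 days = 2.93 years
- 1,156 − 180 = 976 days = 2.67 years

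**Visits affected, earliest possible participant.** If enrolment was Day 1, he was at Day 694 + 1 = 695 on 01-Sep-2017 and Day 1,850 + 1 = 1,851 on 31-Oct-2020.
- Month 24 is Day 721, and its window opens at Day 714. That is after Day 695, so he has no Month 24 value in the truncated table. Anyone starting later is further from it.
- Months 24, 30, 36, 42, 48, 54 and 60 (Days 721, 901, 1,081, 1,261, 1,441, 1,621 and 1,801) all fall between Day 695 and Day 1,851. On the current schedule that is up to 7 laboratory and vital-sign visits.
- ECG: Day 1 and Month 12 (Day 361) are kept. Months 24, 36, 48 and 60 are lost, 4 of 6 on-treatment visits.

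**What still covers the period.** These outputs carry no 2017 cut-off: adverse-event tables, PCSA tables (haematology, blood chemistry, vital signs), low/normal/high laboratory categories, the any-time liver table, the Kaplan-Meier analysis of AST/ALT above 3 × ULN, the eDISH plots, spaghetti plots of actual values for seven laboratory parameters, and listings. None gives change from baseline by visit. For ECG, only listings remain.

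**The case against.** The strongest case for leaving this as a minor inconsistency has four parts.

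**Other outputs catch what matters.** Protocol 9.2.3 requires clinically relevant laboratory, examination and ECG findings to be recorded as adverse events. Antithrombin and peak thrombin are summarised at each visit with no 2017 end date. The seven plotted parameters are those closest to the drug's liver and thrombosis risks. A drift that persisted would show at resumption as change from the LTE14762 baseline. All of this is true and limits the harm. It does not restore 2017–2020 change from baseline for general laboratory and vital-sign data, show a drift that had resolved by restart, or cover participants who never restarted.

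**The ECG limb is weak.** The protocol promises only ECG listings, and the SAP provides them. That stands: for ECG the conflict is within the SAP only.

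**The visit counts are soft.** They describe one hypothetical participant. A Day 1 more than 1,851 − 1,801 = 50 days after enrolment would put Month 60 beyond 31-Oct-2020, and screening may run 60 days. The six-monthly schedule came with Amendment 06 in 2019, whereas Amendment 04 had made Years 2 to 4 monthly, so seven may understate the visits affected. The counts are illustrative, not a tally.

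**Truncation may be deliberate.** Enrolment was staggered, so the hold falls at different study months and later visit columns mix different exposure histories. That would be a fair reason, but the SAP does not give it. The exception clause in SAP 5.2 qualifies the separate analysis of the two regimens; the sentences on the safety period and on pause data carry no exception.

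**Conclusion.** The concern holds. SAP 6.8.3 to 6.8.5 contradict SAP 5.2 and 6.8 and, for laboratory and vital-sign data, Protocol 10.2.6. Neither SAP 2.6 nor SAP 2.7, where departures from the protocol are recorded, mentions the cut-off.

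Followed as written, at least 1,156 calendar days are missing from descriptive tables that serve the primary objective, and no original-regimen column from Month 24 onward is produced. The loss is confined to summaries of level and change from baseline; it is not an absence of safety analysis.

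The day counts rest on the Table 4 reference dates, since the exact hold dates are redacted and individual last-assessment and restart dates vary. The on-drug figure of 2.67 to 2.93 years also rests on the assumed hold length, and the visit counts on enrolment being Day 1 and on the current schedule. The conflict between the sections depends on none of these assumptions. It should be corrected before the tables are produced.

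**What to change.** In SAP 6.8.3, 6.8.4 and 6.8.5, replace the 2017 cut-off with the dose restart date after the 2020 voluntary pause, or last study follow-up for participants who did not restart. This matches SAP 5.2.

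Flag, or show separately, assessments taken during the 2017 hold and the 2020 pause. Define those periods by the safety row of SAP Figure 1, "Starts from the day after last dose date before the hold/pause and in terms of study days", through to resumption. Do not use the efficacy exclusion in SAP 6.3 (intercurrent event I.b), which begins 29 days after the last dose.

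A separate post-hold block would serve equally well if mixing exposure histories is the worry. If the sponsor does intend to omit the period, SAP 2.7 should record this as a departure from Protocol 10.2.6 and give the reason.

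The cost is SAP wording, a hold/pause flag and a rerun of existing tables on data already collected. SAP 5.10 already assigns original-regimen visits from the CRF, so scheduled visits need no new windows. It gives no rule for unscheduled original-regimen visits, so one sentence is needed for any taken during the hold or pause. Post-hold columns will include participants with a past dosing gap, which a footnote can state.

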While local laboratory results may be used for dosing decisions and urgent clinical decisions, on the day of the clinic visit assessments, all laboratory assessments specified in the protocol which are performed at the clinic should also be sent in parallel to the central laboratory. In the case of discrepant local and central laboratory results on samples drawn on the same day with available results, central laboratory results will be relied upon for clinical and dosing decisions.

6.8.4 Vital signs and physical examination

Descriptive statistics will be provided for vital signs, including blood pressure, pulse rate, oral body temperature and respiration rate. For data under the original dose and regimen, the descriptive summary will be provided from the LTE14762 study baseline up to the 2017 clinical dose pause. For data under the revised dose, the summary will be provided from the dose resumption up to the end of study. A summary table of PCSA will be provided. Abnormal PE results will be listed. All the vital sign and physical examination summary tables will not include assessment taken during the major surgery period. These results will be presented in listings with identifier of major surgery.

6.8.5 Electrocardiogram

Listings for 12-lead ECG will be provided. Additionally, PR, QRS, QT, Bazzett's (QTcB) and Fridericia's (QTcF) corrected QT and RR intervals will be summarized descriptively, where (QTcF) is calculated using the formula

$$QTcF \text{ (ms)} = QT \text{ (ms)} \cdot \sqrt[3]{\frac{HR \text{ (bpm)}}{60}}$$

and where (QTcB) is calculated using the formula

$$QTcB \text{ (ms)} = QT \text{ (ms)} \cdot \sqrt{\frac{HR \text{ (bpm)}}{60}}$$

For data under the original dose and regimen, the descriptive summary will be provided from the LTE14762 study baseline up to the 2017 clinical dose pause. For data under the revised dose, the summary will be provided from the dose resumption up to the end of study.

6.8.6 Medical history

Medical history will be summarized by MedDRA(version 25.1 or later) coding system SOC and PT. A participant contributes only once to the count for a given condition (overall, by SOC, by PT).

6.8.7 Concomitant medications

Concomitant medication is defined as all medications other than study drug administered to a participant during the study. (All AE and CM collected in the study should be included in the analyses because all participants received dose in TDR14767(ALN-AT3SC-001).) Concomitant medications will be coded using the WHO Drug Dictionary. Results will be tabulated by anatomic

therapeutic class (ATC) and preferred term. Concomitant medications excluding the medication used during the major surgery period will be summarized. A separate summary of concomitant medication administrated during the major surgery period will also be provided.

6.8.8 Bleed management guidelines

Compliance and deviations from bleed management guidelines (as presented in Table 8 of the Protocol) will be listed and summarized descriptively.

6.9 ANTIDRUG ANTIBODY

ADA will be analyzed similarly as PD after the 1st significant dose. Number of participants testing positive for antidrug antibody (ADA) pre-study-drug (before first study drug dose in TDR14767(ALN-AT3SC-001) study) and post-study-drug administration will be summarized by Hemophilia type (A/B) and incidence of ADA positivity will be presented by frequency and as a percent by Hemophilia type and across all participants. In addition, maximum ADA titer and range of titer values will be presented by hemophilia type and across all participants, if applicable. ADA results will be listed by visit.

